- Obtaining additional tests to evaluate liver function, as appropriate (for example INR, direct bilirubin).
- Considering gastroenterology or hepatology consultations.

Clinically significant out-of-range values must be recorded as an adverse event on an *Adverse Event Report Form*.

The central laboratory will be notified by the sponsor when the biological samples may be destroyed.

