11.1.5 All Adverse Events

All adverse events will be listed for the APES and APES2.

An overview of the PYE, numbers, and percentages of patients with TEAEs, serious adverse events (SAEs), adverse events leading to withdrawal, or patients who died will be provided. For TEAEs, SAEs, and adverse events leading to withdrawal, the total number of events will be included.

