11.2 General Methodology for Other Safety Data

The denominators for the summaries of a given variable will be based on the number of patients with non-missing values at a given visit or during the assessment period.

Descriptive statistics for the safety variables in the open label treatment period, absolute values changes from both Baseline I and Baseline II, will be presented by visit and the last post-baseline assessment in the treatment period.

For the open-label treatment period with memantine, summaries will be presented for absolute values and change from Baseline III by visit and last assessment in the treatment period.

The number and percentage of patients with at least one PCS value at any post-Baseline II assessment in the open-label treatment period will be summarised by variable. The number and percentage of patients with at least one PCS value at any post-Baseline III assessment in the open-label treatment period with memantine will be summarised by variable . All available assessments will be included in the evaluation of PCS values (scheduled, reassessments, and unscheduled). For tests where PCS is defined as a change, the summaries will be prepared both for PCS compared to baseline I and baseline II for the open label treatment period.

For patients with post-baseline II PCS values (compared to baseline II) in the open-label treatment period, listings will be provided including all available values for the variable, with

LU Study Number: 14861B Trial Site Number: Study Level Pluto ID: CLI 00933680

Page 18 of 48

flagging of PCS values and out-of-reference-range values. The corresponding listings will be prepared for the open label treatment period with memantine.

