11.3.2 Urinalysis

For tests based on urine dipsticks, the results are categorical, and the number and percentage of patients will be summarised for each test by visit week and last assessment in each treatment period.

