Appendix IV PCS Criteria

LU Study Number: 14861B Trial Site Number: Study Level Pluto ID: CLI_00933680

PCS Criteria

Table 1 PCS Criteria for Clinical Safety Laboratory Tests

CDISC term	Test (units)	PCS Low	PCS High
Liver			
AST	S-aspartate aminotransferase (IU/L)		$\geq 3 \times ULN$
ALT	S-alanine aminotransferase (IU/L)		\geq 3 × ULN
BILI	S-bilirubin (μmol/L)		≥ 34
BILDIR	S-direct bilirubin (µmol/L)		≥ 12
ALP	S-alkaline phosphatase (IU/L)		$\geq 3 \times ULN$
GGT	S-gamma glutamyl transferase (IU/L)		≥ 200
Kidney			
CREAT	S-creatinine (µmol/L)		$\geq 1.5 \times ULN$
BUN	B-urea nitrogen (mmol/L)		≥ 11
Electrolytes			
SODIUM	S-sodium (mmol/L)	≤ 125	≥ 155
K	S-potassium (mmol/L)	≤ 3.0	≥ 6.0
CA	S-calcium (mmol/L)	≤ 1.8	≥ 3.0
BICARB	S-bicarbonate (mmol/L)	≤ 12	≥ 38
Endocrine/Meta	bolic		
GLUC	Serum glucose (mmol/L)	≤ 3.9	≥ 11.1
GLUC	Serum glucose, fasting (mmol/L)	≤ 3.5	≥ 7.0
TSH	S-thyrotropin (mIU/L)	≤ 0.3	≥ 5.5
ALB	Albumin (g/L)	≤ 27	
Lipids			
CHOL	S-cholesterol (mmol/L)		≥ 7.8
CHOL	S-Cholesterol, fasting (mmol/L)		≥ 6.2
TRIG	Triglycerides (mmol/L)		≥ 5.65
TRIG	Triglycerides, fasting (mmol/L)		≥ 4.2
Haematology/Co	pagulation		
INR	P-INR (Prothrombin ratio)		≥ 2.0
PLAT	B-thrombocytes platelet count (×10E9/L)	≤ 75	≥ 600
HGB	B-haemoglobin (g/dL)	≤ 9.5 (women) ≤ 11.5 (men)	≥ 16.5 (women) ≥ 18.5 (men)
RBC	B-erythrocytes (×10E12/L)	≤ 3.5 (women) ≤ 3.8 (men)	\geq 6.0 (women) \geq 7.0 (men)
WBC	B-Leukocytes (×10E9/L)	\leq 2.8	≥ 16
NEUTLE	B-Neutrophils/leukocytes (%)	≤ 20	≥ 85
EOSLE	B-eosinophils/leukocytes (%)		≥ 10

Page 47 of 48

LU Study Number: 14861B Pluto ID: CLI_00933680

Status: Final

Version: 1.0

CDISC term	Test (units)	PCS Low	PCS High
BASOLE	B-basophils/leukocytes (%)		≥ 10
LYMLE	B-Lymphocytes/leukocytes (%)	≤ 10	≥ 75
MONOLE	B-Monocytes /leukocytes (%)		≥ 15
Infection			
CRP	S-C-reactive protein (mg/L)		≥ 25
Urine			
GLUC	U-Glucose		Increase≥2
KETONES	U-Ketones		Increase≥2
OCCBLD	U-Occult Blood		Increase≥2

Table 2 PCS Criteria for Vital Signs and Weight

CDISC term	Variable (units)	PCS Criterion Low	PCS Criterion High
WEIGHT	Weight (kg)	Decrease ≥ 7%	Increase ≥ 7%
BMI	Body mass index (kg/m2)	Decrease $\geq 7\%$	Increase $\geq 7\%$
DIABP	Supine diastolic blood pressure (mmHg)	\leq 50 and decrease \geq 15	≥ 105 and increase ≥ 15
SYSBP	Supine systolic blood pressure (mmHg)	\leq 90 and decrease \geq 20	≥ 180 and increase ≥ 20
PULSE	Pulse rate supine/sitting/unknown (bpm)	\leq 50 and decrease \geq 15	\geq 120 and increase \geq 15

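### Urine protein is the only one of the four protocol urine tests without a PCS criterion, so a within-patient rise gets no PCS count, PCS listing or PCS-linked adverse event listing

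*SAP*

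**What the plan says.** Protocol 9.4.2, Panel 5 names four scheduled urine tests: protein, glucose, blood and ketones. Protocol 16.9.2 plans to flag and summarise PCS values and names no exempt test.

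SAP Appendix IV, Table 1 ends with a urine block of three rows: glucose, ketones and "U-Occult Blood". Each has a high criterion of an increase of at least 2. Protein does not appear.

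SAP 11.2 makes PCS status the trigger for three outputs:

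- **Incidence.** A count and a proportion are given: "patients with at least one PCS value at any post-Baseline II assessment in the open-label treatment period will be summarised by variable", with a parallel summary after Baseline III. Scheduled, repeat and unscheduled assessments all count.
- **Values.** "For patients with post-baseline II PCS values (compared to baseline II) in the open-label treatment period, listings will be provided including all available values".
- **Adverse events.** A listing of the adverse events of patients with PCS values, with each value placed next to events in the same visit window.

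The reference for change-based criteria is also given: "For tests where PCS is defined as a change, the summaries will be prepared both for PCS compared to baseline I and baseline II".

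Two routes do not need a PCS criterion. SAP 11.3.2 says of urine dipstick tests that "the number and percentage of patients will be summarised for each test by visit week and last assessment in each treatment period". Protocol 9.4.2 says: "Clinically significant out-of-range values must be recorded as an adverse event". SAP 11.1.5 adds: "All adverse events will be listed for the APES and APES2".

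SAP section 17, which records changes from the protocol analyses, mentions only the C-SSRS.

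**The concern.** A change-based PCS rule exists to identify patients who worsened on treatment. Three of the four urine tests have one. The fourth does not, and no reason is given.

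The primary objective of both treatment periods is safety and tolerability. Controlled diabetes and controlled hypertension are allowed at entry (Protocol 5.3), so some patients may already have protein in the urine at baseline. The percentage positive at a visit then mixes existing with new findings. Protocol 3.2 also supports the substudy design by its ability to compare safety within a patient before and after memantine is added. For urine protein, the planned laboratory outputs do not make that comparison.

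**Working it through.** No sample size, power or alpha figure is involved. The check is a row match followed by a trace of which outputs depend on the matched row.

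**Step 1. Match Panel 5 to Table 1 (urine).**

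| Protocol Panel 5 | SAP Table 1 urine row | Criterion |
|---|---|---|
| U-glucose | yes | increase ≥2 |
| U-ketones | yes | increase ≥2 |
| U-blood | yes (occult blood) | increase ≥2 |
| U-protein | none | none |

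Tests 4, criteria 3, unmatched 4 − 3 = 1.

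**Step 2. Match the rest of Panel 5.** The panel lists 8 haematology, 2 lipid, 1 infection, 6 liver, 4 electrolyte, 2 metabolic, 2 kidney, 4 urine and 2 coagulation tests: 8 + 2 + 1 + 6 + 4 + 2 + 2 + 4 + 2 = 31. All have a Table 1 row except U-protein and aPTT, so 31 − 2 = 29 are covered. Protein is therefore the only uncovered urine test, but not the only uncovered test. In the other direction, Table 1 has rows for TSH and erythrocytes, which Panel 5 does not list, and fasting rows for glucose and triglycerides, which Panel 5 labels non-fasting.

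**Step 3. Trace the outputs.**

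| Output | Glucose, ketones, blood | Protein |
|---|---|---|
| Category counts by visit week and last assessment (SAP 11.3.2) | yes | yes |
| Adverse event, if judged clinically significant (Protocol 9.4.2; SAP 11.1) | yes | yes |
| PCS incidence count (SAP 11.2) | yes | no |
| PCS-triggered listing of all values (SAP 11.2) | yes | no |
| PCS-linked adverse event listing (SAP 11.2) | yes | no |

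**Step 4. Can the category counts stand in for the PCS count?** They are marginal counts at each time point. Take two hypothetical patients, graded 0 and 2 at Baseline II. If neither changes, the later visit shows one patient at 0 and one at 2, and nobody has risen by 2. If they exchange grades, the later visit again shows one at 0 and one at 2, but one patient has risen by 2. The table is the same in both cases. No shift table is planned that would separate them.

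There is a second difference. For post-baseline visits SAP 18.3.2 takes the first usable assessment from the scheduled visit, or the Withdrawal Visit assessment if there is none. The PCS count takes all assessments, including repeats and unscheduled tests.

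**The case against.** A reader might infer from the missing row that patients with rising proteinuria are never counted or listed. The documents do not support that. SAP 11.3.2 counts patients in each category by visit and at last assessment. The investigator must review every out-of-range value and record the clinically significant ones as adverse events. An event that starts or increases in intensity after Baseline II is treatment-emergent (SAP 11.1.3), is allocated to its treatment period (11.1.4), is counted per patient by preferred term (11.1.6) and is listed. Proteinuria that the investigator judges significant does reach the tables.

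A reader might also infer a breach of the protocol. Protocol 16.9.2 says that PCS values will be flagged, not that every test will have a criterion. The mismatches in both directions suggest a general list rather than a study-specific row that was dropped, and the choice of tests to threshold is largely the sponsor's.

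Three further points are fair. Panel 5 does not call its urine tests dipsticks; that word is the SAP's, and the link to protein is an inference. The case for consequence is thin: Protocol 1.1.3.3 reports no laboratory trends of relevance in the phase II Alzheimer study apart from liver tests, no renal topic is among the adverse events of special interest, and creatinine, urea nitrogen and albumin keep their PCS rows. Finally, the tables were read from PDF, so a lost row cannot be fully excluded, although no gap is visible between the urine block and Table 2.

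These points limit the concern without removing it. The adverse event route depends on investigator judgement and applies equally to glucose, ketones and blood, for which the SAP still sets a criterion. Nothing in the SAP explains why protein is treated differently.

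**Conclusion.** The point holds in a narrow form and is minor. Protein lacks the three PCS-driven outputs that the other three urine tests have. What is lost is a systematic per-patient count and listing of rises in urine protein that does not depend on the investigator's judgement of significance. Category counts and adverse event reporting remain.

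The number of patients affected cannot be estimated, because the documents give no proteinuria rate. Nothing shows that a primary safety conclusion would change.

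The verdict assumes that Table 1 has been read completely and that protein is reported on a categorical scale like the other urine tests. If it is reported on another scale, it still has no PCS criterion, but the form of the missing rule would differ and the general change-from-baseline summaries in SAP 11.2 would apply to it.

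**What to change.** Add a U-protein row to the urine block of SAP Table 1 with the criterion already used for glucose, ketones and occult blood (increase of at least 2), adapted if protein is not reported on the same categorical scale. Evaluate it against Baseline I and Baseline II in the 28-week period and against Baseline III in the memantine substudy. If the omission is deliberate, one sentence giving the reason would be the minimum.

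The data are already collected and the existing PCS programming can take the row. The cost is a few more patients in the listings. The criterion will not flag a patient who moves up by a single grade, which is also how the other three urine tests are handled.

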Visit	Baseline IIª	,	Treatme	nt Perio	d	Completion/ Withdrawal ^b	Safety Follow-up ^c
Visit Number	1	2	3	4	5	6	7
Day ^d /	0	28/	56/	84/	140/	196/	224/
End of Week		4	8	12	20	28	32
Visit Window ^e (days relative to nominal visit)		± 7d	+ 7d				
Screening/Baseline Proced	ures and As	ssessmen	nts				
Signed informed consent							
Demographics	\sqrt{f}						
Height	\sqrt{f}						
Medical history	\sqrt{f}						
Inclusion/exclusion criteria	\checkmark						
Efficacy Assessments							
MMSE	\sqrt{g}						
ADAS-Cog	\sqrt{g}			\checkmark			
ADCS-ADL ₂₃	\sqrt{g}					V	
ADCS-CGIC ^h	\sqrt{g}						
NPI	\sqrt{g}			\checkmark		\checkmark	
Other Assessments							
RUD Lite	\sqrt{g}			√			
EQ-5D-3L	\sqrt{g}			\checkmark			
Dependence scale	\sqrt{i}			\checkmark		\checkmark	
Safety Assessments							
Adverse events	\sqrt{j}						\sqrt{k}
Blood and urine sampling for clinical safety							
laboratory tests	\sqrt{g}	\checkmark	\checkmark	\checkmark	\checkmark	\checkmark	
Vital signs, weight, ECGs	$\sqrt{\mathrm{g}}$	\checkmark	\checkmark	\checkmark	\checkmark	\checkmark	
C-SSRS	\sqrt{g}	\checkmark	\checkmark	\checkmark	\checkmark	\checkmark	
Examinations (physical, neurological)	\sqrt{g}		\checkmark				
Other Study Procedures							
IMP and donepezil ¹ hydrochloride dispensed							
IMP and donepezil' hydrochloride returned accountability tracked		\checkmark	\checkmark		\checkmark	\checkmark	

Panel 2 Study Procedures and Assessments [open-label treatment period (initial 28-week period)]

Visit	Baseline II ^a	Treatment Period				Completion/ Withdrawal ^b	Safety Follow-up ^c	
Visit Number	1	2	3	4	5	6	7	
Day ^d /	0	28/	56/	84/	140/	196/	224/	
End of Week		4	8	12	20	28	32	
Visit Window ^e (days relative to nominal visit)		± 7d	± 7d	± 7d	± 7d	± 7d	+ 7d	
Screening/Baseline Proced	ures and As	sessmen	its					
Recent and concomitant medication	\sqrt{j}	\checkmark						
Dispense Patient Identification card								
Patient Identification card returned						\sqrt{m}		
Informed Consent Provided [open-label treatment period with memantine (substudy)]					\sqrt{n}			

a. For the purposes of clarity, the Baseline Visit is called Baseline II Visit and this visit is the same as Visit 7 (Completion Visit) in the lead-in study.

- b. This visit should take place as soon as possible after the patient withdraws from the study.

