1.1.2 Non-clinical Data

Idalopirdine is a high affinity antagonist for the 5-HT₆ receptor. Broad profiling of idalopirdine in more than 100 additional assays demonstrated medium affinity to the adrenergic α -1A and α -1B receptors and to the dopamine D3 receptor. Efficacy profiling showed that idalopirdine was an antagonist for the adrenergic α -1A, α -1B and dopamine D3 receptors. For all the remaining targets tested, idalopirdine demonstrated at least 100-fold selectivity.

Idalopirdine has been shown to improve performance in multiple rodent cognition tasks. In doses leading to >65% striatal 5-HT₆ receptor occupancy *in vivo*, idalopirdine reversed

cognitive impairment induced by subchronic phencyclidine in rats. There is no preclinical evidence to demonstrate the cognitive benefits of concomitant treatment of idalopirdine, donepezil and memantine. In microdialysis studies, administration of idalopirdine alone did not affect extracellular levels of GABA, dopamine, 5-HT or acetylcholine (ACh) in the rat prefrontal cortex, whereas idalopirdine (5 mg/kg per os) significantly potentiated donepezil-induced increases in extracellular levels of ACh. This suggests the possibility of synergistic effects when combining idalopirdine with acetylcholine esterase inhibitors.

Safety pharmacology and toxicology studies indicate that at clinically relevant exposure levels, idalopirdine is well tolerated. Multiple-dose toxicology studies were conducted in rats and monkeys at doses up to 250 mg/kg and 50 mg/kg, respectively. In monkeys, convulsions occurred at high exposure levels. In rats, increased blood clotting time was noticed at high exposure levels.

Exploratory data using human recombinant enzymes indicated that cytochrome P450 isoenzyme (CYP) 3A4 was the major CYP450 enzyme involved in the metabolism of idalopirdine with some contribution from CYP1A2, CYP2C9, CYP2C19, and CYP2D6. Idalopirdine showed inhibitory potential towards CYP2D6. Furthermore, in an *in vitro* study evaluating the induction potential of idalopirdine, idalopirdine showed little (CYP2B6 and CYP2C8) or no induction potential (CYP1A2, CYP2B6, CYP2C8, CYP2C9, CYP2C19, CYP2D6 and CYP3A4/5) towards the CYPs investigated.

Further information can be found in the *IB*.¹

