1.1.3.3 Safety

Idalopirdine was safe and generally well tolerated in healthy subjects (young and elderly men and women) following multiple doses up to 300 mg/day with no clinical significant effects on vital signs, clinical laboratory tests or ECG parameters.

In the phase II study, 12936A, conducted in patients with AD, idalopirdine was safe and, with the exception of elevated transaminase values, well tolerated as adjunctive therapy to donepezil in patients with AD at a dose of 90 mg/day (30 mg TID) for 6 months.

In this study, the incidence of treatment-emergent adverse events (TEAEs) was slightly higher in the idalopirdine group (66%) than in the placebo group (59%). The most common adverse events, (occurring in >2 patients and with an incidence of more than 4% and with a >2 times higher incidence in patients treated with idalopirdine than in patients treated with placebo), were γ -glutamyltransferase increased, Alanine aminotransferase (ALT) increased, Aspartate aminotransferase (AST) increased, Dizziness, Headache, Aggression, and Vomiting.

The proportion of patients who withdrew due to TEAEs in this study was 15% in the idalopirdine group and 7.5% in the placebo group. The differential withdrawal was almost entirely due to elevated liver enzymes test values reported as TEAEs.

A total of 14 (9.7%) patients in the idalopirdine group and 13 (9.8%) patients in the placebo group had one or more serious adverse events (SAEs).

There were more patients in the idalopirdine group than in the placebo group who had AST, ALT and/or alkaline phosphatase (AP) values above the upper limit of normal (ULN) at some point during the study. There were no differences between the treatment groups in the incidence of total bilirubin level (TBL) above ULN. A total of 13 patients (all in the idalopirdine group) had AST or ALT values that were >2 times ULN. The elevated liver test values were seen around week 8. For all the 13 patients, the liver test values subsequently decreased towards the reference range. The mechanism behind these increased liver tests is currently unknown.

Except for liver tests, the changes from baseline for all clinical safety laboratory tests and ECGs showed, on average, small fluctuations without clinical relevance and with no trends over time or between the treatment groups.

In the two phase II studies conducted in patients with schizophrenia, idalopirdine was safe and well tolerated for up to 12 weeks.

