9.4.3 Vital Signs

Please refer to Panel 2 and Panel 3 for time-points of assessments.

Assessments done at Visit 7 (Completion Visit) of the lead-in study will be transferred and considered as the Baseline II Visit results.

For patients continuing into the open-label treatment period with memantine (substudy), assessments and procedures done at Visit 6 in the open-label treatment period (initial 28-week period) are the same as the Baseline III Visit.

Blood pressure (BP) and pulse rate will be measured using a standard digital meter after the patient has rested for at least 5 minutes in a supine position. The patient must then be instructed to change from a supine to a standing position in a manner consistent with his/her normal routines and that includes passing through a sitting position before assuming an upright position. BP and pulse rate will be measured after the patient has been standing for at least 1 minute but no longer than 5 minutes.

Measurements are to be obtained for a specific patient in the same manner (preferably from the same arm) throughout the study. Care should be taken to avoid stressful stimuli such as blood sampling immediately prior to measurements.

Abnormalities of clinical significance must be recorded as an adverse event on an *Adverse Event Report Form*.

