Antipsychotics atypical	Only treatment with risperidone (maximum 2 mg/day) or quetiapine (maximum 100 mg/day) is allowed if absolutely necessary, and if prescribed according to treatment guidelines. Risperidone or quetiapine treatment should not be initiated within 3 days of a study visit with efficacy assessments.
Antiviral agents	Anti-HIV agents are disallowed.
Anxiolytics	The use of benzodiazepines as anxiolytic treatment is acceptable, provided the
	dose remains fixed during the study. Where absolutely necessary,
	benzodiazepine treatment can be initiated as a short-term anxiolytic treatment
	during the study, as long as the treatment is not initiated within 3 days of a
	study visit with efficacy assessments.
	Use of antidepressants is described in the corresponding row.
Benign prostate hyperplasia	Only alpha-1 blockers (Terazosin, Tamsulosin, Doxazosin) and finasteride are
Beta-blockers	Precaution should be taken when administering betablockers
Cough/cold agents	Onen-label treatment period (initial 28-week period):
Cough cold ugents	Only non-opioids and codeine allowed.
Diuretics	Open-label treatment period with memantine (substudy): Only non-opioids and codeine allowed. Dextromethorphan disallowed. Open-label treatment period with memantine (substudy): Hydrochlorothiazide and triamterene are disallowed.

Drug Class	Details		
H2 blocker/proton pump	Open-label treatment period (initial 28-week period):		
inhibitors	Dose modifications and initiation of treatment allowed during the study.		
	Open-label treatment period with memantine (substudy):		
	Dose modifications and initiation of treatment allowed during the study, but		
TT ' 1 1' 1	caution should be exercised according to the memantine SmPC.		
Hormones, including hormone-	Dose modifications and initiation of treatment allowed during the study.		
replacement therapy	Steroids: See separate row.		
Hormone suppressants	Dose modifications and initiation of treatment allowed during the study.		
Insulin	Rosiglitazone is disallowed.		
Hypolipidaemics	Dose modifications and initiation of treatment allowed during the study.		
Muscle relaxants	Allowed on a p.r.n. basis (not to exceed 5 consecutive days).		
	As specified in Section 4.5 of the donepezil, rivastigmine and galantamine		
	SmPC precaution should be taken when administering neuro-muscular		
	blockers.		
NMDA-antagonist (memantine)	Open-label treatment period (initial 28-week period):		
	Disallowed during the study.		

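### Standing blood pressure and pulse are collected, but the SAP's potentially clinically significant (PCS) criteria use no standing value and no planned output shows the postural change

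*SAP*

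**What the plan says.** **Collection.** Protocol 9.4.3 has blood pressure and pulse taken "after the patient has rested for at least 5 minutes in a supine position". The patient then stands, and "BP and pulse rate will be measured after the patient has been standing for at least 1 minute", with an upper limit of 5 minutes. Panels 2 and 3 schedule vital signs at Visits 1 to 6 (Visit 1 transferred from the lead-in study) and, in the memantine substudy, at Visits 6 and 8 to 11. The safety follow-up visits (7 and 12) have none.

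**Evaluation.** SAP 11.4 refers to Appendix IV, Table 2 for the PCS criteria. The low criteria there are:
- "Supine systolic blood pressure (mmHg"): at or below 90 with a decrease of at least 20.
- Supine diastolic pressure: at or below 50 with a decrease of at least 15.
- Pulse (supine, sitting or unknown position): at or below 50 with a decrease of at least 15. The high limit is 120 or above with an increase of at least 15.

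SAP 11.2 measures change-type criteria against study baselines. It also plans by-visit summaries of absolute values and changes, without naming body position.

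**Pharmacology.** Protocol 1.1.2 reports that "idalopirdine was an antagonist for the adrenergic" alpha-1A and alpha-1B receptors, with medium affinity.

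**The concern.** The protocol asks for a paired measurement at every scheduled treatment visit. The usual reason for a pair is to look at the difference, yet the SAP never specifies that difference, and its flagging rules ignore one half of the pair.

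Three things in the protocol make this relevant:
- Safety and tolerability are the primary objective in both periods (2.1).
- The drug has alpha-1 antagonism, and 1.1.3.3 lists "Dizziness, Headache, Aggression, and Vomiting" among the adverse events in the phase II Alzheimer's study with an incidence above 4% and more than twice that on placebo.
- Appendix II names other alpha-1 blockers for benign prostate hyperplasia ("Only alpha-1 blockers (Terazosin, Tamsulosin, Doxazosin) and finasteride are" permitted, on the row's plain sense). It also lets most antihypertensives be started or changed during the study.

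At stake is whether the study report can say how large the postural changes were and how many patients had a marked one, using data already in the database.

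**Working it through.** The plan states no figure to reproduce, so the check sets the sections side by side and then applies the Table 2 rules.

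**1. Which outputs could show a fall on standing?**

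| SAP output | Uses standing values or the postural difference? |
|---|---|
| Table 2 PCS criteria | No: supine pressure; supine, sitting or unknown-position pulse |
| Decrease terms in Table 2 (SAP 11.2) | No: change from a study baseline, not from lying to standing |
| Listing of adverse events beside PCS values (SAP 11.2) | Only for patients who already have a PCS value |
| Vital-sign plots (SAP 11.4, Panel 4) | No: weight only |
| Events of special interest (SAP 11.1.11) | No: convulsions, hepatic disorders, haemorrhages |
| By-visit summaries (SAP 11.2) | Not stated |
| Adverse event tables (SAP 11.1) | Indirectly, if the investigator records an event |

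**2. What do the Table 2 rules do with a postural fall?** Assume, for illustration, supine pressure 130/75 and pulse 70, both unchanged from baseline.

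| Systolic fall on standing | Standing systolic | Supine systolic rule | Supine diastolic rule | Pulse rule |
|---|---|---|---|---|
| 20 | 130 − 20 = 110 | not met | not met | not met |
| 30 | 130 − 30 = 100 | not met | not met | not met |
| 40 | 130 − 40 = 90 | not met | not met | not met |
| 60 | 130 − 60 = 70 | not met | not met | not met |

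The reason is the same in every row. The systolic rule needs supine ≤ 90 and baseline minus supine ≥ 20; here supine is 130 and the change is 130 − 130 = 0. The diastolic rule sees 75 (not ≤ 50) and a change of 0. The pulse rule sees 70 (neither ≤ 50 nor ≥ 120) and a change of 0. By contrast, a supine fall from 130 at baseline to 90 is flagged, since 90 ≤ 90 and 130 − 90 = 40 ≥ 20. The result does not depend on the assumed values: a standing reading is not an input, so it cannot alter the outcome.

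**3. Would by-visit summaries fill the gap?** If standing values were included, standing mean minus supine mean would give the average postural change in patients with both readings. The number of patients with a large individual fall could not be recovered, because separate summaries of the two positions do not retain the pairing.

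**4. Is there a reference value?** Protocol 9.4.3 transfers the lead-in Visit 7 vital signs as Baseline II, and 3.2 says the safety assessments match those of the lead-in studies. A paired Baseline II value should therefore exist. In former placebo patients it precedes any idalopirdine. The lead-in protocols were not available to confirm this.

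**The case against.** A reader might infer that orthostatic hypotension would go undetected. The documents do not support that. Protocol 9.4.1 and 9.4.3 require clinically significant vital-sign abnormalities to be recorded as adverse events. Those events then reach the tables by preferred term, intensity and causality and, where they apply, the serious-event, withdrawal and dose-reduction outputs. This stands. What remains is that the route depends on investigator judgement, and that symptoms are elicited by a non-leading question in patients with dementia.

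A reader might also infer that a postural effect of the drug is likely. The affinity is described as medium. Protocol 1.1.3.3 reports no clinically significant effect on vital signs in healthy subjects, including the elderly, at multiple doses up to 300 mg/day, which is 300/60 = 5 times the 60 mg/day used here. The dizziness finding comes from 90 mg/day, with an estimated mean peak concentration of 540 ng/mL against 390 ng/mL for 60 mg once daily (1.1.3.1), and nothing links it to posture. Patients whose abnormal vital signs the investigator considers a safety risk are excluded from both periods (5.3). All of this stands: the pharmacology makes the check relevant but does not show harm.

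Two further points are fair. SAP 18.2 derives rating-scale scores only and gives no derivation for BMI or QTcF either, so its silence on posture proves little. SAP section 16 also relies on sponsor standards that were not available. The point therefore rests on the content of Table 2 and SAP 11.2 and 11.4. Finally, Protocol 16.9.2 promises no postural analysis, so this is an omission and not a contradiction between protocol and SAP.

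**Conclusion.** The point holds as a gap in the PCS evaluation and is worth fixing because it is cheap. Under the plan as written, no fall confined to the standing reading can be PCS, and none can bring a patient into the listing of adverse events beside PCS values. That follows from the definitions and needs no assumption about patients.

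It is tempting to state what share of postural falls would be missed overall. The documents give no distribution of supine pressure or postural change in this population, so any such percentage would reflect only the values chosen, and none is offered here. It is equally tempting to reuse Table 2's 20 and 15 mmHg limits for posture. Those are changes from a study baseline, applied together with an absolute limit, and nothing in the documents supports them as lying-to-standing cut-offs.

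The conclusion assumes that the sponsor's unseen output standards do not already add a postural table.

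**What to change.** 1. Derive standing minus supine for systolic pressure, diastolic pressure and pulse at each visit with both readings.
2. Summarise these by visit. Also tabulate each patient's largest postural fall after Baseline II and after Baseline III, for example in 10-mmHg bands, against the postural change at the corresponding baseline.
3. State body position in all vital-sign summaries.
4. Add a postural PCS flag to Table 2 with a cut-off that the sponsor pre-specifies and justifies for this purpose, and let it feed the existing listing of adverse events beside PCS values.

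The cost is a few derived variables and one more table, with no new procedure or visit. The limit is interpretive: with no concurrent control, the table cannot separate a drug effect from age, dementia or co-medication, and should be presented as descriptive.
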